### Précis

Chronic hepatitis B is a major cause of cirrhosis, end-stage liver disease and hepatocellular carcinoma and affects approximately 1.25 million Americans. Six medications have been licensed for use in chronic hepatitis B in the United States, but their relative benefit and long-term efficacy remain unclear. In previous studies, we have shown that maintained suppression of HBV DNA can be achieved with nucleoside analogues and that suppression is associated with marked improvements in disease. In this randomized study, we propose to evaluate long-term therapy with tenofovir alone or in combination with emtricitabine (FTC). Forty treatment-naïve patients with chronic hepatitis B will be enrolled in the primary study. After medical evaluation and liver biopsy, patients will be stratified by hepatitis B e antigen (HBeAg) status and randomized to receive either tenofovir alone or in combination with FTC. Treatment will be continued long-term (at least four years) and patients will be carefully monitored for side effects, serum aminotransferase and HBV DNA levels. Patients will undergo repeat liver biopsy and assessment of antiviral resistance at 1 and 4 years. The primary endpoint of therapy will be the maintained suppression of HBV DNA to below  $10^2$  IU/ml (lower limit of detection of current assays). The study will assess the relative efficacy and safety of combination versus mono-therapy. A separate group of 60 previously treated patients will also be enrolled and randomized to mono- or combination-therapy to assess the safety profile of these agents. The primary analysis will be conducted on the entire study cohort.

[Word count = 250]

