term maintenance therapy for patients with chronic hepatitis B (both HBeAg-positive and -negative). The results of this trial will be compared to historical controls from a NIH trial evaluating the combination of lamivudine and adefovir versus adefovir monotherapy and published multicenter randomized control trials of lamivudine and adefovir for HBeAg positive chronic hepatitis B. The primary endpoint of this trial will be a maintained suppression of HBV DNA below  $10^2$  IU/ml and secondary endpoints will be normalization of serum ALT levels and improvement in histological features of chronic hepatitis. A separate group of patients will be treated with either tenofovir alone or tenofovir and emtricitabine as a “salvage” protocol for patients who have received nucleoside analogue therapy and have failed to have complete viral suppression despite at least 48 weeks of therapy or who have relapsed following withdrawal of therapy. This “salvage” arm will allow for further evaluation of safety and viral suppression and will be used in the primary analysis of response to tenofovir monotherapy vs. combination therapy of tenofovir and emtricitabine.

**Hypotheses and Issues:** This protocol will address the following questions.

Treatment naïve patients:

1. Will combination therapy using tenofovir and emtricitabine have superior antiviral effects against HBV compared to tenofovir alone? To address this issue, HBV DNA and ALT levels will be monitored frequently and both the absolute decrease and the slope (kinetics) of decrease will be compared. The investigators believe that the patterns of decrease of HBV DNA and ALT levels will be similar between tenofovir and combination arms, the pattern reflecting the more potent activity of tenofovir and the absence of a synergy or additive effect of these two nucleos(t)ide analogues.
2. Will combination therapy prevent or delay the appearance of antiviral resistance to tenofovir? To address this issue, the HBV polymerase gene will be sequenced from all serum samples at yearly intervals that are HBV DNA positive. Rates of development of mutations shown to be associated with tenofovir resistance (rtA194T) will be compared between the combination and monotherapy arms. The investigators believe that the rate of antiviral resistance will be low and that at 4 years, 20-25% of patients in the monotherapy arm but no patients in the combination arm will exhibit genotypic antiviral resistance.

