#### A1. Inclusion criteria: Primary Study (nucleoside analogue-naïve subjects)

- 1) Age >18 years and older, male or female
- 2) Known serum HBsAg positivity for 24 weeks
- 3) Detectable HBV DNA > $10^4$  IU/ml. For patients with cirrhosis HBV DNA > $10^3$  IU/ml
- 4) Serum ALT or AST levels 1.5 X ULN (for ALT:  $\geq 62$  U/L and for AST:  $\geq 46$  U/L) based on at least two determinations taken at least one month apart during the 24 weeks before study entry; no ALT requirement for patients with cirrhosis
- 5) Liver biopsy within 2 years of entry that is consistent with chronic hepatitis and with a histology activity index (HAI) score of 4 or more (scores range from 0-18) and an Ishak fibrosis score of at least 1 (scores range from 0-6). For patients who have had a liver biopsy at another institution, slides must be obtained for reading and scoring at the NIH.
- 6) Written informed consent

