### C. Initial evaluation

Patients will be seen in the outpatient clinic of the NIH Clinical Center and undergo the following evaluation before starting therapy. Patients requiring a liver biopsy will be admitted to the Clinical Center for a percutaneous liver biopsy under ultrasound guidance.

1. History and physical examination.
2. Blood tests – complete blood count (CBC with differential and platelet count), prothrombin time, partial thromboplastin time, sedimentation rate, Chem-20 (which includes alanine aminotransferase [ALT], aspartate aminotransferase [AST], direct and total serum bilirubin, albumin, total protein, lactic dehydrogenase [LDH] creatine phosphokinase [CK], sodium, chloride, bicarbonate, potassium, blood urea nitrogen, creatinine, uric acid, calcium, and phosphorus), alpha-fetoprotein, amylase, lipase, immunoglobulin G, A and M, thyroid stimulating hormone (TSH), antinuclear antibody (ANA), rheumatoid factor, lipid panel (triglycerides, total cholesterol, high density lipoprotein associated cholesterol, low density lipoprotein associated cholesterol), hepatitis B viral markers (HBsAg, anti-HBs, HBeAg, and anti-HBe), anti-HCV, anti-HDV, and anti-HIV. An additional 10 ml. of serum will be collected and stored at –20 degrees Celsius for future research testing.
3. Baseline HBV DNA level by quantitative PCR (Amplicor™: Roche, lower limit of detection 20 IU/ml) and HBV genotyping (HBV Genotyping Line Probe Assay, Innogenetics, Belgium).
4. Routine urinalysis, random total protein/creatinine ratio, and two 24-hour urines for creatinine clearance and protein excretion.
5. Pregnancy test for women of childbearing potential.
6. Patients who have not had them within the previous year will undergo chest X-ray, electrocardiogram (EKG), and abdominal ultrasound.

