Patients will be seen in the outpatient clinic at weeks 0, 2, 4, 8, 12, 24, 36, and 48 weeks during the first year of therapy and at 12 week intervals thereafter.

At 48 weeks, all patients will be readmitted to the NIH Clinical Center and undergo a repeat thorough medical evaluation and liver biopsy. Patients in the salvage arm will be excluded from undergoing the 48 week liver biopsy. Continuation of therapy thereafter will depend upon both tolerance and benefit. All patients will undergo a 192 week follow-up biopsy to assess long-term efficacy and durability of response. Benefit is described in Section F “Assessment of Response” and tolerance in Section G “Assessment of Toxicity.”

The side effects will be monitored regularly. Tenofovir and emtricitabine will be stopped if moderate side effects attributable to either or both medications develop and persist for at least one week or on repeat testing. The medication(s) can be restarted if the adverse event resolves and does not appear to be related to either or both medications.

In the absence of toxicity attributable to either agent, combination therapy with tenofovir and emtricitabine or monotherapy with tenofovir will be continued for 192 weeks. Study medication/s will be discontinued if there is serological evidence of resolution of chronic hepatitis B, as shown by loss of HBsAg, documented on two serum samples taken at least six months apart.

Patients on therapy who develop evidence of drug resistance with elevations of serum aminotransferase levels twice above normal and HBV-DNA levels greater than  $10^6$  IU/ml will be switched to alternative therapies if mutually agreed between the patient and the investigators.

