### **E. Monitoring**

Patients will be seen, interviewed, and have blood and urine tests taken at regular intervals according to the following schedule (Appendix A): on at least two occasions during the six months before treatment (Screen 1 and 2) including at the time of liver biopsy and initial evaluation, on day 0 (before first administration of drug) and at weeks 2, 4, 8, 12, 24, 36, and 48 after starting therapy. Thereafter, the patients will be seen every 12 weeks while on therapy. At each visit, the patients will be asked about symptoms and possible side effects and fill out a symptom and side effect questionnaire. Blood samples will be drawn for CBC and biochemical tests including chemistry-20 panel (ALT, AST, alkaline phosphatase, creatine kinase, lactic dehydrogenase, direct and total bilirubin, sodium, potassium, chloride, bicarbonate, glucose, BUN, creatinine, albumin, total protein, calcium, and phosphate), and 10 ml of research blood. HBV DNA will be measured at every clinical visit during therapy and more often if needed, such as to investigate viral breakthrough. In addition, HBsAg, HBeAg and anti-HBe will be tested every 12 weeks during therapy and anti-HBs if appropriate. An additional sample will be collected for routine storage to allow for repeat testing. Urine will be collected for urinalysis and random total protein/creatinine ratio at every visit. Twenty-four hour urine for creatinine clearance and total protein will be done at 48 weeks and 192 weeks. Women of child bearing potential will have a pregnancy test at each study visit. Women with a positive pregnancy test will be immediately withdrawn from study drug/s. Patients may be offered alternative approved therapy if clinically indicated. Immunological testing for CD4+ and CD8+ T cell responses to HBV antigens will be done before treatment for all previously untreated patients and repeated at 2, 4, 8, 12, 36 and 48 weeks for HLA-A2 positive patients. Alpha-fetoprotein levels will be measured every 24 weeks. Ultrasound or computerized tomography of the liver will be done every 24 weeks months in patients with advanced fibrosis or cirrhosis; in other patients these tests will be done at the time of 48 and 192 week liver biopsies. Fibroscan of the liver will be performed yearly. Bone mineral density will be re-assessed at 48 and 192 weeks.

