## I. Statistical analysis

Superiority of combination therapy compared to monotherapy with tenofovir will be tested. The primary analysis will be conducted at 1 and 4 years on the entire study cohort (Groups A-D). A separate analysis will be conducted on previously treated subjects with resistance combining all HBeAg-positive and -negative cases. We predict the rate of full virological response to combination therapy will be 94% and to tenofovir monotherapy to be 70% at 4 years. A Fisher's exact test with a .05 two-sided significance level will have 86% power to detect the difference between a combination therapy proportion of  $\pi_1$  of .94 and a monotherapy proportion of  $\pi_2$  .70 if the sample size in each group is 50. Secondary analyses will be done within the HBeAg positive and negative stratum and the nucleos(t)ide naïve and nucleos(t)ide treated stratum. Variables to be analyzed in association with a virological response will include: baseline ALT and HBV DNA level, liver histology, HBV genotype and previous resistance. Patients with missing data or who drop out of the study will be considered as treatment failures on an intention to treat basis. For comparison of means, Student's t-test will be used. All reported p-values will be 2-sided.

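### HBV DNA fall and slope are compared with no time window and no rule for undetectable values; done at week 48 or later, this would largely track baseline and understate a true difference in potency

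*Combined protocol and SAP*

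**What the plan says.** Hypotheses and Issues, treatment-naïve patients, item 1, asks whether tenofovir plus emtricitabine has a greater antiviral effect than tenofovir alone. HBV DNA and ALT are to be followed often, and "both the absolute decrease and the slope (kinetics) of decrease will be compared". No window, scale or estimator is given. The investigators expect the two arms to behave alike, with no additive effect.

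The other passages that bear on this are:

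- **Assay limit.** Section C, item 3, gives the PCR assay a "lower limit of detection 20 IU/ml". The Précis calls 10^2 IU/ml the "lower limit of detection of current assays", and Section F also treats values below 10^2 as undetectable.
- **Entry level.** Section A1 requires HBV DNA above 10^4 IU/ml. "For patients with cirrhosis HBV DNA" need only exceed 10^3. There is no upper limit.
- **Method.** Section I says "For comparison of means, Student's t-test will be used". It has no rule for values below detection. Baseline viral load appears as a predictor of response ("Variables to be analyzed in association with a virological response will include: baseline ALT and HBV DNA level"), not as a covariate for fall or slope. Missing-as-failure fits only a binary outcome.
- **Timing.** Section F designates weeks 48 and 192 for formal analysis; Section I says 1 and 4 years. In the first year patients are seen "at weeks 0, 2, 4, 8, 12, 24, 36, and 48 weeks" (Section D), and "HBV DNA will be measured at every clinical visit during therapy" (Section E).

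**The concern.** Once a patient is at the assay floor, the recorded fall is baseline minus a constant, whatever further suppression the drug achieves. A line fitted through floor values flattens, and it flattens soonest in patients who started low or responded fastest, so the better responder can show the smaller slope. An analyst who follows the plan literally could take fall or slope at the only formal analysis times, when most patients are expected to be suppressed. A real difference in potency would then be hard to see. Because similarity is the expected finding, an apparently confirmatory result could not be told apart from the effect of the floor.

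**Working it through.** **1. The plan's own figure.** Section I gives 86% power for Fisher's exact test, 0.94 against 0.70, 50 per arm, two-sided 0.05. Exact enumeration gives 85.7%, so it reproduces. It concerns the binary primary endpoint; no power is stated for fall or slope.

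**2. Ceiling on the recorded fall (no assumptions).** Maximum fall = log10(baseline/limit).

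| Baseline, IU/ml | Limit 20 | Limit 10^2 |
|---|---|---|
| 10^3 | 1.70 | 1.00 |
| 10^4 | 2.70 | 2.00 |
| 10^6 | 4.70 | 4.00 |
| 10^8 | 6.70 | 6.00 |

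The two stated limits differ by log10(100/20) = 0.70 log10. The same 0.70 is the whole range in which a full responder's value can lie above a floor of 20, so among responders the recorded fall is baseline minus a near-constant.

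**3. How much difference is lost (simulation).** From the documents: the visit weeks, the floor of 20 IU/ml, and about 20 naïve patients per arm (the Protocol section's minimum of 40; Section D gives at least 60 for the same groups while capping each of the two at 20). Assumed, because the documents give no figures:

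- mean baseline 5.0 to 6.5 log10 in HBeAg-negative and 6.5 to 8.5 in HBeAg-positive patients, SD 1.0, minimum 4;
- first-phase fall 2.0 log10 (SD 0.4), then 0.10 log10 per week (SD 0.03);
- assay SD 0.2;
- combination arm 20% faster.

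Values below 20 were set to 20, and fall and least-squares slope were compared by t-test. Ranges run across the low, middle and high baseline scenarios.

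| Fall at | Values below 20 | True difference, log10 | Observed | Share kept | R² on baseline | Power without floor → with floor |
|---|---|---|---|---|---|---|
| Week 4 | 0–5% | 0.45–0.46 | 0.43–0.45 | 95–100% | 0.03 | 76–80% → 75–78% |
| Week 12 | 4–26% | 0.64–0.65 | 0.48–0.61 | 73–95% | 0.03–0.16 | 85–88% → 66–83% |
| Week 24 | 23–59% | 0.88–0.90 | 0.34–0.66 | 38–75% | 0.13–0.56 | 79–83% → 18–60% |
| Week 48 | 70–92% | 1.36–1.40 | 0.08–0.33 | 6–24% | 0.66–0.93 | 69–75% → 1–7% |

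Without a floor, R² on baseline is 0.02–0.03 throughout. Slopes keep 95–100% of the difference over weeks 0–4, 68–95% over weeks 0–12, 24–70% over weeks 0–24, and −16% to 13% over weeks 0–48, so the sign can reverse.

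**4. Sensitivity.** With a slower second phase (0.06 log10 per week, SD 0.02, middle baseline), week 48 keeps 43% of the difference, R² is 0.48 and power falls from 72% to 18%; week 12 keeps 92%. A separate simulation under assumed baselines and decline rates kept about 5–23% at week 48.

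**5. No true difference.** The floored t-tests rejected in 1–6% of runs, so false positives are not raised.

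**6. Does a censored model help?** A left-censored normal model with baseline as covariate, 300 runs per cell:

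- week 12 recovers 0.63–0.64 of 0.63–0.66 log10 (power 82–89%);
- week 24 recovers 0.79–0.85 of 0.87–0.89 (power 60–78%);
- week 48 recovers only 0.80–1.07 of 1.31–1.39 (power 24–36%).

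Censoring repairs the early window well but cannot rescue week 48. In a separate simulation with 20 per arm, a censored model had type I error of 5.5–8.5%.

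**The case against.** The strongest reply is that nothing in the documents places this comparison late. Item 1 speaks of frequent monitoring and of kinetics, and the visits at weeks 0, 2, 4, 8 and 12 suit an early analysis, where the floor does little harm. Fall and slope are in none of the endpoint lists. The t-test sentence is general and is not tied to them. All of this is true, and it limits the point. But the plan fixes no early window either, and the formal times that it does name are those where the floor matters most.

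A reader might infer that fall and slope cannot be derived at all, or that the comparison as planned mostly measures baseline viral load. The documents do not support either: early values are usable, floor values are censored rather than lost, and dominance by baseline appears only in late or whole-year analyses (and not clearly even then if decline is slow).

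A reader might also take the predicted 70% and 94% response rates as the share of naïve patients at the floor. Those are 4-year predictions for the whole-cohort analysis, and for values below 10^2 rather than below 20 IU/ml. Nearer evidence is the Background's report that all seven tenofovir-treated patients were below 10^2 within 24 weeks, but they had been treated before.

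Finally, late means need not be equal. If non-responders sat at 10^4 IU/ml (assumed) and responders at the floor, the predicted rates would give (0.94 − 0.70) × 2.70 = 0.65 log10. That reflects response rate, which item 3 already addresses, and power at 20 per arm would be 17–54% for an SD of 2.0 down to 1.0.

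**Conclusion.** The concern stands in a limited form. The plan leaves open a comparison of fall or slope at week 48 or later, or over the whole first year, that would be largely determined by baseline in patients at the floor and would pull a true difference toward zero. The ceiling arithmetic rests only on the stated floor. The size rests on assumed baselines and decline rates: roughly 5–25% of the difference in fall kept at week 48 in the main scenarios, 43% with slower decline. Week 4 is almost untouched; week 12 loses little unless baselines are low.

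It would go too far to infer that the analysis must confirm similarity whether or not it is true. At week 4 the plain t-test still has 75–78% power for the assumed 20% advantage. The cost is power and bias toward no difference, not false positives, and the binary primary endpoint is unaffected. The change is worth making because a t-test at the plan's formal times would answer item 1 materially worse than data already being collected allow.

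**What to change.** For item 1, state in Section I:

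- Compare log10 HBV DNA fall and slope over a fixed early window, weeks 0 to 12, using the scheduled visits at weeks 0, 2, 4, 8 and 12.
- Adjust for baseline HBV DNA and HBeAg status, and treat values below the detection limit as left-censored.
- Take the p-value from a permutation test, since the censored model can be slightly anti-conservative at about 20 per arm.
- Do not test fall or slope by t-test at week 48 or later; report time to HBV DNA below 10^2 IU/ml instead.
- Give one detection limit throughout, reconciling 10^2 IU/ml in the Précis with 20 IU/ml in Section C.

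The cost is a few sentences and slightly more programming, with no new samples or visits. The price in interpretation is that the kinetic conclusion covers the early phase only.

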- 1) Will combination therapy yield a higher response rate and prevent the development of further resistance than monotherapy in patients with previous antiviral resistance (lamivudine, adefovir and entecavir)? Response will be defined as HBV DNA  $<10^2$  IU/ml and normal ALT at 48 and 192 weeks. Samples of blood at yearly intervals that are HBV DNA positive will be tested for tenofovir (rtA194T) and emtricitabine (rtM204V/I and rtL180M) resistant mutations by direct sequencing. The investigators believe that the maintained virological and biochemical response will be higher in the combination arm compared to the monotherapy arm and the rate of further resistance will be lower at 48 and 192 weeks.

Patients who relapsed after withdrawal of lamivudine, adefovir or the combination of lamivudine plus adefovir:

- 1) We hypothesize that combination therapy will result in a greater proportion of subjects re-responding to re-institution of therapy. Response will be defined as an HBV DNA  $<10^2$  IU/ml and normal ALT at 48 and 192 weeks. For individuals who experienced HBeAg sero-reversion (HBeAg negative to positive) a response will also include loss of HBeAg or HBeAg seroconversion again. We further hypothesize that

combination therapy will prevent or delay the appearance of antiviral resistance compared to tenofovir monotherapy in persons who relapsed? To address this issue, the HBV polymerase gene will be sequenced from all serum samples at yearly intervals that are HBV DNA positive.

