The primary study endpoints will be a maintained full virological response after 48 weeks and 192 weeks of therapy (the two points of formal statistical analysis). The major secondary endpoint will be absence of a failure of therapy and absence of resistance mutations. Other endpoints to therapy will be loss of HBeAg, loss of HBsAg, normalization of serum ALT, improvements in histology activity index, improvements in hepatic fibrosis, improvement in Fibroscan scores and decrease in HVPg. Other endpoints will be improvement in symptom scores at 48 and 192 weeks.

Failure of therapy may be due to primary non-response, lack of virological response, breakthrough, or relapse, as defined below.

A **primary non-response** is defined as lack of decrease in HBV DNA levels by at least 1  $\log_{10}$  after at least 24 weeks of therapy in the absence of non-compliance.

A **failure in virological response** is defined as failure to suppress HBV DNA below  $10^4$  IU/ml after 48 weeks of therapy in the absence of non-compliance.

A **breakthrough** is defined as a  $\geq 1 \log_{10}$  IU/L increase in HBV DNA level from nadir in two consecutive samples at least one month apart in a patient with an initial full virological response in the absence of non-compliance.

A **relapse** is defined as a rise in HBV DNA levels to above  $10^4$  IU/ml or of ALT to above the normal range after therapy is stopped in a patient who previously had a maintained full virological response.

These definitions are all interlocking but help to define response and non-response rates and whether therapy has a sustained effect.

**Stopping therapy:** Therapy will be continued indefinitely or until one of the following endpoints are reached:

1. **Failure of therapy:** If HBV DNA levels remain consistently  $>10^4$  IU/ml after one year of continuous therapy, patients will be offered alternative therapy or the option to stop therapy. Alternative therapies may include switching to combination therapy if they were receiving monotherapy or switching to entecavir if receiving combination therapy. Patients who fail to respond may also elect to receive a course of peginterferon. These options are available at the NIH Clinical Center on an open-label basis.

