## **H. Viral resistance**

Tenofovir resistance is defined phenotypically as: (1) rise in serum HBV-DNA levels to levels above  $10^4$  IU per ml (by quantitative PCR) after they had fallen below this level during therapy in patients who have been compliant with their regimen and genotypically as (2) documented mutation/s in the reverse transcriptase region of the HBV polymerase gene (thus far the only documented mutation is rtA194T), and biochemically as (3) rise in serum aminotransferases to twice the upper limit of normal range. Patients who develop resistance will be continued on the therapy if they agree to stay on therapy and if serum aminotransferases and HBV-DNA are consistently lower than pretreatment levels or changed to other available agents if clinically indicated.

Emtricitabine resistance in this study can only be defined phenotypically as a rise in serum aminotransferases to twice the upper limit of normal range. Genotypic resistance is defined by the typical mutations in the conserved catalytic region of the HBV polymerase gene (YMDD region).

Monitoring for mutations in the reverse transcriptase domain of the HBV-DNA polymerase on combination therapy will be performed on serum samples obtained at baseline, and yearly on all serum samples that have detectable HBV DNA from patients receiving tenofovir plus emtricitabine and tenofovir monotherapy. The monitoring will be done by sequence analysis of the reverse transcriptase region of the HBV DNA polymerase gene and will be performed by LDB, NIDDK. Novel mutations will be correlated with the clinical response. Antiviral susceptibility and cross resistance testing using in vitro assays will be conducted by Gilead Sciences using stored serum samples. Resistance data will be submitted to the FDA according to the FDA guidance document entitled, "Guidance for submitting HBV Resistance Data."

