#### **O. Research Use, Storage and Disposition of Human Samples and Data:**

Patients will have serum stored from selected time points during this study. These specimens will be used for repeat virological testing and special tests as needed (such as for viral levels, HBV genotype or serotype, HBV DNA sequence or testing for serum levels of cytokines or interferon induced genes). Samples may be used to assess factors associated with response or non-response to antiviral therapy. Liver biopsy tissue may be stored if a biopsy is done before therapy and if residual tissue is available after routine samples are taken for routine histological staining and evaluation. These samples will be tested in the Liver Diseases Branch or the routine clinical and surgical pathology services of the Clinical Center. Stored serum will be used to perform in vitro antiviral susceptibility and cross resistance testing. Gilead Sciences will conduct these assays and serum samples will not contain any patient identifiers. Samples will be sent as soon as virologic breakthrough is identified and Gilead will have one year after receipt of the sample in which to provide LDB, NIDDK with the results. Research records and data as well as liver biopsy slides, biopsy reports, liver tissue and sera with the patient's name and a unique identifier will be stored indefinitely in our locked offices and freezers, the medical record department and the pathology department. These materials will be protected and tracked by standard operating procedures in the medical record and pathology departments as well as a compulsive filing system in our locked offices and freezers. There will be redundant storage of clinical information in the medical record department and our offices. Likewise, there will be redundant storage of biopsy information and materials in the pathology department and our offices. This should minimize the risk of loss or destruction of information and specimens. If that were to occur we would report it to the IRB. We do not plan to destroy this personal medical information or the liver biopsy specimens or research subject sera after completion of the

study because it may be critically important for physicians (here or elsewhere) to have access them when caring for these patients in the future.

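### Yearly sequencing can miss resistance mutations in patients who leave the randomised drug between yearly samples; sequence stored serum at confirmed breakthrough and before any change

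*Combined protocol and SAP*

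**What the plan says.** **Endpoint.** Section F (Assessment of response) states: "The major secondary endpoint will be absence of a failure of therapy and absence of resistance mutations". Hypotheses and Issues asks separately whether combination therapy prevents or delays tenofovir resistance in naïve patients. It expects genotypic resistance in 20–25% on monotherapy and in none on combination at 4 years. Similar questions are put for previously resistant patients and for relapsers.

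**Sequencing.** For naïve patients: "To address this issue, the HBV polymerase gene will be sequenced from all serum samples at yearly intervals that are HBV DNA positive". For previously resistant patients: "Samples of blood at yearly intervals that are HBV DNA positive will be tested for tenofovir (rtA194T") and for the emtricitabine mutations. Section H (Viral resistance) says that mutation monitoring "will be performed on serum samples obtained at baseline, and yearly on all serum samples that have detectable HBV DNA", and limits this to patients on the two study regimens.

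**Visits.** Sections D and E set visits every 12 weeks after week 48, with HBV DNA measured at each visit and more often if breakthrough is being investigated.

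**Change of drug.** Under section D, patients with evidence of resistance, aminotransferases twice above normal and HBV DNA above 10^6 IU/ml "will be switched to alternative therapies if mutually agreed between the patient and the investigators". Under section H, resistant patients may continue if they agree and their values stay below pre-treatment levels, or may be changed to another agent if clinically indicated. Neither rule refers to a yearly sample.

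**Other testing.** Section O says of breakthrough: "Samples will be sent as soon as virologic breakthrough is identified and Gilead will have one year after receipt of the sample". That testing is in vitro susceptibility and cross-resistance. Section O also lists HBV DNA sequence among the possible uses of stored serum, as needed.

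**Scoring.** Section I counts missing data and dropouts as treatment failures. No rule covers resistance status after a change of drug.

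**The concern.** The mutation comparison is meant to describe what happened on the randomised drug. Its sampling follows the calendar, while a change of drug follows the patient's course. A patient whose virus rebounds and who is moved to another regimen between yearly samples reaches the next one after some weeks of different treatment. If HBV DNA is then undetectable, nothing is sequenced. If the patient has moved to a drug outside the two study regimens, section H read literally no longer covers the sample. If a monotherapy patient has moved to combination, the sequence is obtained on the other arm's regimen.

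Because the protocol expects no resistance on combination, undetected cases would fall almost entirely on monotherapy and shrink the observed difference. The question of whether combination prevents or delays tenofovir resistance could then be answered too cautiously, on a small number of events.

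**Working it through.** **1. The plan's own figure.** Section I gives 86% power for Fisher's exact test (two-sided 0.05, 0.94 v 0.70, 50 per arm). Exact enumeration over the two binomials gives 85.7%, so the figure reproduces. It concerns HBV DNA suppression. No power is stated for resistance.

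**2. Which visits are exposed.** Scheduled visits after week 48 fall at weeks 60, 72, …, 192: (192 − 60)/12 + 1 = 12. Three of these (96, 144, 192) are yearly samples, leaving 9 that are not.

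- If a rebound is confirmed at the next scheduled visit and the drug is changed only then, first rebounds at weeks 84, 132 and 180 are confirmed on a yearly sample. Exposed visits are 60, 72, 108, 120, 156 and 168: 6/12 = 50%.
- If confirmation uses an unscheduled draw before the next visit, weeks 84, 132 and 180 are exposed too: 9/12 = 75%.

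These bounds assume onset spread evenly over the visits after week 48. First-year onsets are not counted.

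**3. Share missed.** Let f be the exposed share (0.50 or 0.75), s the probability that the drug is changed before the next yearly sample, and c the probability that this sample then fails to show the mutation. The missed share is m = f × s × c. The documents give neither s nor c, so both are assumptions:

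- s = 0: m = 0.
- s = c = 0.5: m = 0.125 (f = 0.50) or 0.1875 (f = 0.75).
- s = c = 1: m = 0.50 or 0.75, the upper bounds.

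**4. Effect on the p-value.** The Protocol section gives at least 40 naïve patients, about 20 per arm. The expected monotherapy cases are 20 × 0.20 = 4 to 20 × 0.25 = 5. With k cases against none, the two-sided Fisher p is 2·C(20,k)/C(40,k):

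- 5 v 0: 2 × 15,504/658,008 = 0.047
- 4 v 0: 2 × 4,845/91,390 = 0.106
- 3 v 0: 2 × 1,140/9,880 = 0.231

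**5. Effect on power.** Exact Fisher power for resistance, with combination at 0% and monotherapy at the true rate × (1 − m):

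| Per arm | True rate | m = 0 | m = 0.25 | m = 0.50 | m = 0.75 |
|---|---|---|---|---|---|
| 20 | 20% | 37% | 17% | 4% | <1% |
| 20 | 25% | 59% | 32% | 10% | <1% |
| 30 | 20% | 57% | 29% | 7% | <1% |
| 30 | 25% | 80% | 50% | 16% | 1% |
| 50 | 20% | 95% | 78% | 38% | 4% |
| 50 | 25% | 99% | 93% | 61% | 9% |

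The 30-per-arm rows reflect section D, which gives at least 60 naïve patients and conflicts with the Protocol section. The 50-per-arm rows assume that the naïve-patient rates apply to the whole cohort.

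**The case against.** The case against narrows the point considerably, and much of it stands.

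- **Trigger.** A reader might infer that any patient who breaks through can be switched at the next visit. The documents do not say so. Breakthrough in section F is a 1 log10 rise. Section D asks for evidence of resistance, aminotransferase and HBV DNA thresholds, and agreement. Section H lets some resistant patients continue, and they reach the next yearly sample on the randomised drug.
- **One-year failures.** The section F rule for HBV DNA persistently above 10^4 IU/ml mainly concerns patients who are already viraemic at week 48, which is a yearly sample.
- **Failure is still counted.** Breakthrough is listed as failure of therapy, so these patients do not vanish from the major secondary endpoint. Only its mutation part and the separate resistance questions are exposed.
- **Mutants may persist.** A monotherapy patient moved to combination stays on tenofovir, and the mutation may still be found later. This lowers c; it does not make it zero.
- **Cumulative definition.** If section H's phenotypic, genotypic and biochemical criteria must all be met, evidence of resistance would presuppose a sequence. The schedule provides none between yearly samples, so this reading also needs the wording changed.
- **Batch reading.** Section H could mean that every positive sample is sequenced once a year, which would remove most of the gap. The wording for previously resistant patients, which refers to blood samples at yearly intervals, points the other way.
- **Existing provisions.** Stored serum may be sequenced as needed, and breakthrough samples go to the drug supplier. Neither is tied to the mutation endpoint, and the supplier's testing is not described as sequencing.
- **Small numbers.** At 20 per arm, power for resistance is only 37–59% with nothing missed, and no powered test of resistance is planned. The p-values in the working are therefore an illustration.

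**Conclusion.** The point holds as a cheap improvement to a secondary comparison. Sequencing is yearly, a change of drug is not tied to a yearly sample, and no section requires a sequence first. The genotypic comparison could therefore be biased toward no difference.

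The size is unknown. Between 0 and about 50% of onsets after week 48 could be missed if confirmation waits for the next scheduled visit, and up to 75% with an unscheduled draw. Either upper bound also requires every exposed patient to change drug before the next yearly sample and every mutation then to be missed. At 20 per arm, losing one of five expected cases moves p from 0.047 to 0.106.

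Two stronger readings are not supported. A reader might infer that missed resistance will be scored as absent, but the documents contain no scoring rule; that silence is part of the gap. A reader might also infer that the trial's main result is at risk, but the primary endpoint is HBV DNA suppression, and neither it nor its 86% power depends on sequencing.

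**What to change.** In Hypotheses and Issues (naïve question 2, and the items for previously resistant patients and relapsers) and in section H:

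1. Keep the baseline and yearly sequencing, and say whether yearly refers to the sample date or to batch testing of all positive samples.
2. Add sequencing, from serum already stored, of the confirmed-breakthrough sample and of the last HBV DNA-positive sample before any switch, addition or stop of the randomised drug.
3. Count these results in the resistance endpoint together with the yearly ones.
4. State how resistance is scored after a change of drug, and that post-change samples are not used to declare resistance absent on the randomised drug.

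The cost is a wording change and a few extra sequences in the same laboratory, with no extra visit or blood draw. No change to any clinical switching rule is proposed.
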